Hypothesis

Targeted patient education in the form of "Strategic patient education" ¹ in relation to an interdisciplinary, multimodal and patient activating intervention at Rigshospitalet, Clinic for Spinal Cord Injuries (CSCI), is expected to contribute to a decrease of cardiovascular risk factors and maintenance of PA and healthy diet after discharge from the primary rehabilitation.

Purpose

The aim of this Ph.D project is to get an overview of the course of BMI among newly injured people with SCI in Denmark which serves as a historic control in conjunction with a systematic multimodal, intervention study, adapted to a Danish national setting with the aim of reducing cardiovascular risk factors and facilitating PA and healthy diet among all newly injured people with SCI during the primary rehabilitation and after discharge.

Designs (Design description for each sub study).

Sub study 1. Prospective representative longitudinal national survey of Body Mass Index.

Sub study 2. An interdisciplinary multimodal longitudinal controlled intervention study

[figure not shown]
Sub study 3. Test- retest reliability of VO2 peak

Sub study 4. Test-retest reliability of a multi sensor accelerometer.

Methods

¹ Defined as face-to-face interaction between the patient and health care professionals in order to facilitate the patients skills working towards a goal, that requires active patient participation related to decisions for one self and adherence to these. (See description under subproject 2)

Timeline for the project and used outcome measures

Usual rehabilitation today

Usual care during primary rehabilitation today before the intervention study (sub study 2), consists of interdisciplinary rehabilitation provided by doctors, nurses, physio- and occupational therapists, psychologist and social workers with every single profession contributing with their expertise.

According to the masterplan for patient care ("Patientforløbsbeskrivelsen" at Clinic for Spinal Cord Injuries (CSCI)) the patients neurological status (ISNCSCI), level of functioning (SCIM III), bowel and bladder function, cardiovascular and pulmonary function, medication, and psychological state is assessed at admission to CSCI. Non-SCI specific nutritional screening, assessment of body weight and screening for health related outcomes (diet, smoking, alcohol and exercise) is performed as well, but without a systematic approach and follow up.

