Although health promotion related to weight, diet, smoking, alcohol intake and physical activity is part of the usual rehabilitation in CSCI, a systematic approach, follow up and feedback is not provided. Assessment of metabolic profile, body composition and physical capacity is not part of the usual care. In the masterplan for patient care at CSCI, health promoting initiatives are described as "communication and conversation with a health promoting purpose with the patient on a daily basis". How the communication is carried out in practice, and whether some health care professionals have a particular responsibility or expertise related to certain aspects of health promotion eg. based on tests or assessments of health, is unclear and not described in detail. A well described and systematic approach related to health care promotion may ensure that all patients at CSCI receive information and knowledge related to health promotion and the risk of cardiovascular disease.

Sub projects

The project consists of a prospective national survey in collaboration with Spinal Cord Injury Centre of Western Denmark and an intervention at CSCI (see the timeline), which results in 4 sub projects

Sub project 1. Prospective representative national survey of Body Mass Index.

This study includes all patients with a new SCI hospitalized at CSCI or Spinal Cord Injury Center of Western Denmark during a period of 9 months whereby 100 patients are expected to participate. On the basis of usual rehabilitation today, data concerning BMI, level of functioning (SCIM III) and neurological status (ISNCSCI) are collected at admission and discharge. At CSCI BMI is collected every 6 weeks. Also the data for quality of life (QoL SCI), depression (PHQ-2), PA (LTPAQ-SCI) and self-assessed ability to be physically active (ESES) will be collected during this period and at follow up 6 months after discharge. A VO₂peak test at discharge is performed and in some patients measurements of accelerometry (AH) will be performed. Patients with a new SCI who are admitted for rehabilitation several months after the time of injury are also included in the prospective survey. Therefore the data for BMI at the time of injury is collected for all patients at admission to primary rehabilitation from both the patient journal and also by asking the patient about weight and height at the time of injury. Data from this subproject serves as a historic control in the Ph.D project.

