Sub project 2. A systematic interdisciplinary multimodal intervention which, as a part of usual care, facilitates PA, healthy diet and maintenance after discharge through strategic patient education, with the aim of decreasing cardiovascular risk factors.

This pre- post study includes all patients with a new SCI who are admitted at CSCI during a period of 12- 18 months including follow up. Complete data sets from admission to follow up is expected for approximately 50-60 patients during this period. The multimodal, interdisciplinary, patient activating and patient supportive intervention will be a part of usual care during the project period, and all newly injured patients will receive all the multimodal components, or parts of them, dependent on eg. the level of injury. Rehabilitation of the physical level of functioning and physical capacity will take place unchanged as usual.

A central part of the intervention is to create a uniform and systematic approach when the patients receive information and instructions about cardiovascular risk factors, PA and a healthy diet through targeted strategic patient education, which includes targeted, individualized and systematic, face- to-face interaction between patients and health care professionals, while working towards, and improving a specific health related outcome through adherence to the working processes, medicine and lifestyle. The concept has been used previously for patient education and prophylaxis of catheter related sepsis [44]. Strategic patient education is carried out by all the health care professions in different settings with a focus on clarifying the importance of PA and a healthy diet. This will take place during the individual functional training and rehabilitation in general, and in conjunction with feedback about outcome measures and tests with subsequent instructions. Strategic patient education will also be integrated as a concept in the education of the interdisciplinary health care professionals and mentors with a SCI, as they will be implementing the content of the education into a daily clinical setting.

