Data from the patient journals in Epic and the different outcome measures used, is stored in a web based database (Redcap) which is created by the regional Centre for IT, Medico and Telephony (CIMT), with limited access and ID- code, to which pseudo anonymized data is transferred directly,

or via an encrypted USB-stick. An identification list is stored in a locked cabinet at CSCI, local 3403.

Data is stored until December 31, 2027 after which paper material is shredded and data files are deleted.

Statistics

The intervention study and follow up is performed as a pragmatic study and includes, with a few exceptions, all newly injured patients with SCI admitted to primary highly specialized rehabilitation at CSCI. Patients will be included during a time period of 18 corresponding to approximately 40 – 60 patients. Due to the rareness of the morbidity a power calculation is not performed for the primary outcome prior to the intervention, but it is assumed that the total participant number in the intervention and in the historic control cohort, will be comparable to the existing scientific literature.

Numeric continuous data collected at admission, discharge and follow up is reported descriptively as mean and standard deviation together with 95% confidence intervals, or as median, upper and lower quartile as well as interquartile range. Changes over time is reported on the basis of paired t-test. In subproject 3 and 4 the reliability of the outcome measures is analyzed by paired t-test, Pearsons product moment correlation and coefficient of variation or Intraclass correlation coefficient between the test- retest sessions.

Participants, inclusion- and exclusion criteria

Inclusion criteria: All newly injured patients within the previous 12 months, with a SCI and admitted at CSCI are included, regardless of age, neurological level of lesion and completeness of the injury. In subproject 1 all newly injured people with SCI admitted at VCR are also included. Patients under the age of 18 will participate if informed consent is retrieved from their parents.

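### Sub study 2 is called controlled, but the only test of change that Statistics names is a within-patient paired t-test, which cannot separate a programme effect from background VO₂peak recovery

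*Protocol*

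**What the plan says.** All places are in the Protocol.

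- **Designs** lists "Sub study 2. An interdisciplinary multimodal longitudinal controlled intervention study".
- **Purpose** and **Sub project 1** give the survey cohort its role: "Data from this subproject serves as a historic control in the Ph.D project". That cohort is recruited at two centres, "during a period of 9 months whereby 100 patients are expected to participate".
- **Hypothesis** states the question. The education programme "is expected to contribute to a decrease of cardiovascular risk factors and maintenance of PA and healthy diet after discharge from the primary rehabilitation".
- **Sub project 2** uses another label, "This pre- post study includes all patients with a new SCI who are admitted at CSCI", and adds: "Rehabilitation of the physical level of functioning and physical capacity will take place unchanged as usual".
- **Outcome measures** makes VO₂peak the primary outcome.
- **Statistics** refers to the historic control once, in the sentence explaining why no power calculation was made. For change it says: "Changes over time is reported on the basis of paired t-test". The other methods named there belong to the reliability sub projects 3 and 4.
- **VO₂peak in the control cohort.** Sub project 1 says "A VO₂peak test at discharge is performed", and Recruitment of participants confirms that discharge is the only time point at CSCI.

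**The concern.** The project asks whether the programme does something. A paired t-test asks whether the same patients differ between two time points. The answers coincide only if nothing would have changed without the programme, and the protocol's own Background suggests otherwise for the primary outcome. It cites a 24% VO₂peak increase early in rehabilitation and a further increase one year after discharge.

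If the plan is followed as written, a significant paired result on VO₂peak could not be read as a programme effect. The control cohort, collected for that purpose, would enter no named comparison. The timing of control data also limits later repair: with no admission test in the controls, change in VO₂peak cannot be compared between cohorts, whatever a later analysis plan says.

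**Working it through.** The protocol states no power, alpha, SD or effect size, so there is no figure of its own to reproduce. The figures below illustrate scale, with two-sided 5% assumed throughout.

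**1. What the paired test picks up**

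Inputs: n = 40 to 60 (Statistics); a rise of 24% (Background, a literature figure). The SD of individual changes, as a percentage of the admission mean, is not given.

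The test gives p<0.05 when the observed mean change exceeds t(0.975, n−1)/√n SDs of change:

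| n tested | t | limit in SD of change | SD above which a 24% rise is not significant |
|---|---|---|---|
| 40 | 2.023 | 2.023/√40 = 0.320 | 24/0.320 = 75% |
| 60 | 2.001 | 2.001/√60 = 0.258 | 24/0.258 = 93% |
| 25 (assumed) | 2.064 | 2.064/√25 = 0.413 | 24/0.413 = 58% |
| 30 (assumed) | 2.045 | 2.045/√30 = 0.373 | 24/0.373 = 64% |

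The last two rows allow for patients whom the exclusion criteria bar from the exercise test.

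The same point as power (noncentral t), with no programme effect and a true background rise of 24%: the chance of p<0.05 at n = 40 to 60 is 84% to 96% if the SD of change is 50%, and 32% to 45% if it is 100%. Both SDs are assumptions. These are correct rejections of no change, so the test's error rate is not at fault.

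**2. What the control cohort can support**

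| Outcome | Control data listed | Possible comparison |
|---|---|---|
| VO₂peak | Discharge only | Discharge values |
| BMI, SCIM III | Admission and discharge | Discharge adjusted for admission |
| DEXA, metabolic profile | None | None |
| Diet (NORMON) | Not in Sub project 1; Recruitment unclear | To be clarified |

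**3. Precision of a discharge comparison**

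The CSCI share of the 100 controls is not given, so control numbers are assumed:

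- Nine months of controls against an intervention period read as 18 months (Statistics gives 18 without a unit): 40 × 9/18 = 20 to 60 × 9/18 = 30.
- Sub project 2 gives 12 to 18 months including follow-up. Taking off the six-month follow-up leaves at most about 12 months: 40 × 9/12 = 30 to 60 × 9/12 = 45. The third scenario below, with 50 controls, lies somewhat above this.

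The 95% CI half-width is t(0.975, n₁+n₂−2) × √(1/n₁ + 1/n₂). For 40 v 20 it is 2.002 × 0.274 = 0.55 SD. The detectable difference is from the two-sample t-test, 80% power, noncentral t, unadjusted:

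| Scenario (intervention v control) | Detectable difference, SD | CI half-width, SD |
|---|---|---|
| 40 v 20 to 60 v 30 | 0.78 to 0.63 | 0.55 to 0.44 |
| About 25% untestable: 30 v 15 to 45 v 22 | 0.91 to 0.74 | 0.64 to 0.52 |
| Half of the 100 controls tested at CSCI: 40 v 50 to 60 v 50 | 0.60 to 0.54 | 0.42 to 0.38 |

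**The case against.** The strongest reply is that this is an omission. The sentence on paired t-tests speaks of changes over time and does not claim to be the effect analysis. Nothing in Statistics excludes a cohort comparison, and the model for one is commonly left to a statistical analysis plan, which may exist. That stands as regards the absence of a model. It does not dispose of the point: the protocol sets an effect question, assembles a control for it, and then names one test of change that cannot answer it. Collecting control VO₂peak only at discharge also fixes what any later plan can do.

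Several stronger readings are tempting, and the documents do not support them:

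- **That the pre-post and controlled labels contradict each other.** A pre-post study can have a historic control. The difference is one of wording.
- **That the timing of outcomes is in open conflict.** Outcome measures says everything is collected three times, but Recruitment states the VO₂peak exception outright.
- **That the planned article promises a VO₂peak effect.** Its title speaks of effects, but VO₂peak is not visible in the list of outcomes. The link rests on VO₂peak being the primary outcome.
- **That controls certainly have no diet data.** Recruitment describes NORMON being handed out at CSCI and names only VO₂peak as different for subproject 1, so it can be read either way.

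It is also fair to say that a discharge comparison is itself confounded. Controls have no admission value. Intervention patients will already have done the test once, and controls are tested twice at discharge for the reliability study.

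**Conclusion.** The concern holds, as something that should be fixed. The within-patient test is valid for describing course, but it cannot carry the effect question in the hypothesis for an outcome that, on the protocol's own evidence, may rise under usual rehabilitation. The conclusion rests on some background change existing. It does not rest on the value of 24%, since the protocol says the Danish course is not known. The SDs of change, the numbers tested and the CSCI share of controls are assumptions that give scale only.

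A reader might infer that the paired test is invalid or inflates the false-positive rate. It does neither: it correctly detects change. The error would lie in attributing that change to the programme.

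**What to change.** 1. In Statistics, keep the paired t-tests as a description of course, and state that within-cohort change alone will not be reported as a programme effect.
2. Name the between-cohort analysis of the primary outcome: the difference in discharge VO₂peak between the intervention cohort and the CSCI patients of sub project 1, with a 95% CI. Use the controls' first discharge test. Adjust for a few variables collected in both cohorts (for example lesion level and AIS, admission SCIM III, ergometer), no more than the number of tested controls supports.
3. For outcomes collected at admission and discharge in both cohorts (for example BMI, SCIM III), compare discharge values adjusted for the admission value, using CSCI controls only or a centre term.
4. Report outcomes with no listed control data (DEXA, metabolic profile) as descriptive only, and say whether NORMON is collected in sub project 1.
5. State the limits: a non-randomised historic control, no control admission VO₂peak, and intervention patients already familiar with the test.

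The cost is wording, since all these data are already planned, and lower precision: a detectable difference of about 0.54 SD (60 v 50) to 0.91 SD (30 v 15). The range can be narrowed once the protocol gives the CSCI share of the 100 controls and reconciles the intervention period between Sub project 2 and Statistics.

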The prevalence of overweight among people with SCI is high and is conservatively estimated to 66% [4]. In a Swedish cohort of wheelchair dependent people with paraplegia, 27- 36% had a cardiovascular risk profile requiring treatment. When Body Mass Index (BMI) adjusted to SCI was entered into the risk model, 80% had a risk profile requiring treatment [5]. Energy expenditure decreases significantly the first weeks after injury and remains low throughout the primary rehabilitation, with the possibility of decreasing even more the following years. Body fat and body weight also decreases in the acute phase, before increasing in the subacute phase towards the same level as before the time of injury [6]. A longitudinal study with participants ranging from 19-60 years of age and neurological level AIS A-D (54% where incomplete at follow up), found an average loss of lean body mass corresponding to 20,5 and 15, 1% in the lower extremities and trunk respectively during the first year after injury. The course among people with SCI during and after discharge from the primary rehabilitation in Denmark is not known. BMI increases gradually, and especially during the first years after discharge from the primary rehabilitation. A Dutch prospective cohort study found that BMI increased gradually with a prevalence of overweight of 28 % during the primary rehabilitation and 54 % at follow up 5 years after discharge [7]. Similar inventories do not exist for people with SCI in Denmark. Obese people with SCI achieve a lower level of functioning during primary rehabilitation than people with normal weight [8], and more knowledge about prevention, treatment and managing overweight among people with SCI is warranted among health care professionals in the clinical setting. [9]. Overweight in people with SCI is associated with increased risk of depression, while physical activity may contribute to a decreased prevalence of depression and increased quality of life [10, 11]. The relationship between these variables in a Danish setting is not known.

Impact of physical activity on health and fitness

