Bodyweight: Is measured as Body Mass Index (BMI) which is the most widely used outcome measure for measuring bodyweight in people with SCI. BMI is not sensitive enough to distinguish between fat mass and lean body mass nor overweight in people with SCI. Lowering the cut-off for overweight to 25kg/m² the sensitivity increases although this adjustment is not used consequently in the literature [30]. BMI is already collected as part of the existing routines every week and data for BMI every 6th week until discharge will be included in the project. Some newly injured are admitted to primary rehabilitation several months after the time of injury, and the course of bodyweight may already have changed significantly since the time of injury. Therefore BMI at the time of injury is collected from the patient journal from the initial hospitalization during the acute stage and by asking the patient at admission to primary rehabilitation about the height and weight at the time of injury.

Body composition: Is determined by Dual energy x-ray absorptiometry (Dexa) which is gold standard for assessing obesity and body composition although cut-off values for people with SCI has not been established [30].

Metabolic profile: Consists of CRP as a marker for inflammation, BP, Lipid profile: Total cholesterol, Triglycerides, HDL cholesterol, LDL cholesterol which all are included in the International SCI Endocrine and Metabolic Function Basic Data Set, as well as Hemoglobin A1c as

a marker for carbohydrate metabolism, and is included in the International SCI Endocrine and Metabolic Extended Data Set [31, 32].

Level of functioning: Is determined by the Spinal Cord Injury Independence Measure III (SCIM III) which is a valid and reliable outcome measure designed to assess level of functioning in people with SCI in a clinical setting and in research [33] [34, 35]. The SCIM is composed of 19 items that assess 3 domains. 1 Self-care (6 items, scores range from 0-20). 2 Respiration and sphincter management (4 items, scores range from 0-40). 3 Mobility (9 items, scores range from 0-40). The total SCIM scores range from 0 to 100. SCIM III is already collected as part of the existing routines at CSCI.

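### Sub study 1 aims at the course of BMI, but the only method named for change is a paired t-test, whose pooled result also depends on when after injury patients were admitted

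*Protocol*

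**What the plan says.** The Purpose section wants the project to "get an overview of the course of BMI among newly injured people with SCI in Denmark which serves as a historic control". Sub project 1 expects 100 patients over 9 months from two centres and collects BMI at admission and discharge. It adds: "At CSCI BMI is collected every 6 weeks".

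On entry it states: "Patients with a new SCI who are admitted for rehabilitation several months after the time of injury are also included in the prospective survey". The inclusion criteria allow injury up to 12 months earlier. The protocol sees that this affects BMI. Under Bodyweight it notes that "the course of bodyweight may already have changed significantly since the time of injury", and Sub project 1 draws the consequence: "Therefore the data for BMI at the time of injury is collected for all patients at admission to primary rehabilitation". The sources are the patient journal and the patient's own account.

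The background section on the course of overweight cites a study on the shape: "Body fat and body weight also decreases in the acute phase, before increasing in the subacute phase towards the same level". On this population it says: "The course among people with SCI during and after discharge from the primary rehabilitation in Denmark is not known".

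The Statistics section gives descriptive summaries for admission, discharge and follow-up, and then: "Changes over time is reported on the basis of paired t-test". The other methods named there serve the two reliability sub studies. No pairs are listed, and injury-time BMI, the 6-weekly values and time since injury are not mentioned.

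**The concern.** The protocol identifies a timing problem and collects data to deal with it. The one method it then fixes for change takes no account of timing. A paired test compares two visits. If patients reach admission at different stages after injury, the pooled mean change reflects both the course of BMI and the admission mix. Where weight first falls and then recovers, one patient may contribute a fall and another a rise although both follow the same curve.

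Two things are at stake. The survey could report a mean change that does not describe the course it set out to describe. And because these data also serve as the historic control, a later BMI comparison could be shifted by a difference in admission timing alone.

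**Working it through.** **1. Plan figures.** There is none to reproduce. The protocol gives no SD for BMI, no effect size and no distribution of time since injury. The 100 patients are expected recruitment.

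**2. Data against analysis.**

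| BMI value | Collected in sub study 1 | Analysis named in Statistics |
|---|---|---|
| Injury | all patients | none |
| Admission | yes | descriptive; paired t-test |
| Every 6 weeks | CSCI only | none |
| Discharge | yes | descriptive; paired t-test |
| 6 months after discharge | unclear | descriptive; paired t-test |

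The last row is unclear because Sub project 1 lists BMI at admission and discharge and ties follow-up to the questionnaires, while Outcome measures says that every outcome is also collected at follow-up.

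**3. Assumed curve, for illustration only.** Let BMI fall by 1.5 kg/m2 to a turn at month T, then recover over 6 months. Change from injury at month t is −1.5·t/T before T, and −1.5 + 1.5·(t − T)/6 after it, capped at 0.

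Two patients with T = 2 and a stay of 2.25 months:
- Admitted at 0.5 months: −0.375 at admission, −1.3125 at discharge, change −0.94.
- Admitted at 4.5 months: −0.875 at admission, −0.3125 at discharge, change +0.56.

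The curve is the same and the signs are opposite. With T = 0.5 the same two patients change by +0.56 and +0.50, so admission time hardly matters.

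**4. Pooled change.** Early admission is assumed uniform over 1–4 weeks (0.23–0.92 months), late admission over 3–6 months, and stay over 1.5–3 or 3–5 months. Pooled change = w × (mean early change) + (1 − w) × (mean late change), where w is the early share. For T = 3 and the short stay the two means are −1.03 and +0.56, so w = 90% gives 0.9 × (−1.03) + 0.1 × 0.56 = −0.87. The gap between cohorts with early shares of 50% and 10% is 0.4 × the absolute difference of the two means.

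| Turn (month) | Stay (months) | w = 10% | w = 50% | w = 90% | Gap, 50% vs 10% |
|---|---|---|---|---|---|
| 0.5 | 1.5–3 | +0.42 | +0.41 | +0.39 | 0.01 |
| 0.5 | 3–5 | +0.53 | +0.66 | +0.80 | 0.13 |
| 1 | 1.5–3 | +0.42 | +0.15 | −0.11 | 0.27 |
| 1 | 3–5 | +0.58 | +0.44 | +0.29 | 0.14 |
| 2 | 1.5–3 | +0.41 | −0.15 | −0.72 | 0.56 |
| 2 | 3–5 | +0.70 | +0.20 | −0.30 | 0.50 |
| 3 | 1.5–3 | +0.40 | −0.23 | −0.87 | 0.64 |
| 3 | 3–5 | +0.77 | +0.06 | −0.64 | 0.71 |

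For early shares of 50% and 40% the gap is a quarter of the last column, at most 0.18. With the turn at month 1 and the early group admitted at 1–2 months, so that everyone enters after the turn, the 50% vs 10% gap is 0.03 to 0.15. The effect does not need two distinct groups: with lognormal admission times (log-SD 0.8, cut at 12 months), medians of 1 and 2 months give gaps of 0.15 to 0.50 for turns at months 1 to 3.

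**5. Would an injury-to-admission pair help?** Only in part, because that interval also varies. For T = 3 the mean changes are −0.2875 (early) and −1.125 (late), so the 50% vs 10% gap is 0.4 × 0.8375 = 0.335. Turns at months 1 and 2 give 0.10 and 0.18.

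**6. Do the remedies work?** Two separate checks, with turns at months 1 to 3:
- Regressing admission-to-discharge change on a spline of time from injury to admission, plus length of stay, took the 50% vs 10% gap from 0.14–0.70 to between −0.01 and 0.01 (groups of 60 and 50).
- A mixed model on time since injury (n = 100, two centres, 6-weekly values at one) was off by up to 0.26 kg/m2 at month 1 and up to 0.20 elsewhere. It moved by at most 0.08 between early shares of 50% and 10%. Recall error was not simulated.

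**The case against.** The strongest reply is that this is detail for an analysis plan, which may exist but is not shown. For the unlisted pairs and the unnamed analyses taken alone, that is right. What remains is that the protocol itself fixes a method for change, and that method does not fit its own aim and data.

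Second, the course can fairly be read along the rehabilitation pathway. The background section and the planned article title both frame it that way, and paired changes answer that question. This stands, and it is why they should be kept. But the protocol collects BMI at injury precisely because admission is not a common starting point.

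Third, a reader might infer that the protocol expects weight to fall and then rise in this cohort, so that the pooled change will mislead. The documents do not support that. The shape is cited background, placed in the acute phase, and the Danish course is stated to be unknown. If that phase is mostly over before rehabilitation starts, the effect is small.

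Fourth, a reader might infer that the comparison with the historic control is biased. No between-cohort BMI test is named, the primary outcome is VO2peak, and both cohorts take newly injured patients with few exceptions. A swing from 50% to 10% early admissions has no support in the text. With 50% and 40% the gap is at most 0.18.

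**Conclusion.** The point holds as a mismatch between aim, data and stated method. That conclusion rests on the text and needs no simulation. Admission-to-discharge change is valid as a pathway summary. By itself it does not describe the course of BMI when entry may fall anywhere in the first 12 months after injury, and it sets aside two series collected for the purpose.

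Its size is unknown. Under the assumed curves, pooled change runs from +0.80 to −0.87 kg/m2 depending on turn, stay and admission mix. The sign does not change with admission mix when the turn is at half a month, or at month 1 with long stays. It would be wrong to conclude that the paired t-test is invalid or that the survey will report the wrong direction. This is a worthwhile and cheap improvement, not a flaw that undermines the study.

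**What to change.** In Statistics, for BMI in sub study 1:
- Keep the paired changes as pathway summaries and list the pairs.
- Add a linear mixed model with a flexible time-since-injury term, patient random effects and centre, using the BMI values already planned (injury, admission, 6-weekly at CSCI, discharge). Report estimates at fixed times since injury with 95% confidence intervals.
- Repeat it without recalled injury-time values.
- Reconcile Sub project 1 with Outcome measures on whether BMI is collected at follow-up in sub study 1, and include follow-up only where it is.
- If BMI is later compared with the historic control, adjust for time from injury to admission and length of stay.

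If a separate analysis plan already does this, a reference to it is enough.

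The cost is the date of injury for each patient and some more analysis work. Estimates in the first months will be imprecise and somewhat smoothed: with a 10% early share and n = 100, the SD at month 1 was 0.24 to 0.34 kg/m2, besides the error of up to 0.26 shown above. In-stay data are sparser at the second centre. An average recall error in injury-time BMI would shift every change counted from injury.
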